2 INTRODUCTION

[figure not shown]
2.1 Study rationale

Systemic lupus erythematosus (SLE) is a chronic autoimmune inflammatory disease which can present with a chronic disease course but has more often a relapsing-remitting disease course. The majority of patients develop tissue and organ damage over time with current SOC medication due to either lack of well controlled disease activity or due to toxicities of the SOC medications. Therefore, new therapies are needed to achieve long-term control of the disease activity of SLE with well tolerated SLE medication. The study aims to evaluate the efficacy of DZP in study participants who have persistent active or frequently relapsing-remitting SLE with moderate to severe disease activity despite being on stable non-biological SOC medication and therefore have an unmet medical need for a treatment intervention with new therapies.

2.2 Background

This
document
is
for
internal
use
only

2.3 Benefit/risk assessment

The totality of the evidence from studies with clinical and immunological outcome parameters suggests a signal of superior efficacy of DZP in combination with SOC as compared with SOC alone in patients with persisting active or frequent relapsing-remitting SLE.

Risks from taking part in the studies will be minimized through the selection of an appropriate dose level, selection of appropriate study participants defined by the inclusion/exclusion criteria, an independent data monitoring committee (IDMC), regular safety monitoring, and regular blinded assessments of study data assessments.

Overall, the benefit-risk profile of DZP is considered favorable for further clinical development in a Phase 3 program. Further information can be found in the Investigator's Brochure (IB).

3 OBJECTIVES AND ENDPOINTS

Table 3-1: Objectives and endpoints

Objectives	Endpoints
Primary	

To evaluate the ability of DZP as an add-on treatment to SOC medication to achieve clinically relevant long term improvement of moderate to severe disease activity	
Achievement of BICLA response at Week 48
Key Secondary	

To evaluate the ability of DZP as an add-on treatment to SOC medication to achieve fast, clinically relevant improvement of moderate to severe disease activity	
Achievement of BICLA response at Week 24Achievement of BICLA response at Week 12

To evaluate the ability of DZP as an add-on treatment to SOC medication to achieve long term control of disease activity	
Achievement of prevention of severe BILAG flares (severe BILAG flare-free) through Week 48

To evaluate the ability of DZP as an add-on treatment to SOC medication to achieve and maintain the treat-to-target goal: low disease activity with low/acceptable corticosteroid dose over time	
Achievement of LLDAS in $\geq 50\%$ of post Baseline visits through Week 48

To evaluate the ability of DZP as an add-on treatment to SOC medication to achieve improvement of disease activity as measured by numerical disease state score commonly used in clinical practice	
Change from Baseline in SLEDAI-2K at Week 48
Secondary	

To evaluate the ability of DZP as an add-on treatment to SOC medication to achieve components of the composite primary endpoints	
Achievement of BILAG improvement without worsening at Week 48Change from Baseline in PGA at Week 48

To evaluate the ability of DZP as an add-on treatment to SOC medication to achieve alternative responder endpoint	
Achievement of SRI4 response at Week 48

Objectives	Endpoints

To evaluate the ability of DZP as an add-on treatment to SOC medication to achieve endpoints supporting other key secondary endpoints	
Achievement of prevention of moderate/severe BILAG flares (moderate/severe BILAG flare-free) through Week 48Time to severe BILAG flare through Week 48Time to moderate/severe BILAG flare through Week 48

To evaluate the safety and tolerability of DZP as add-on treatment to SOC medication	
TEAEs, serious TEAEs, TEAEs of special interest, and TEAEs of special monitoring
Tertiary	
	
Achievement of reduction of corticosteroid dose from $>7.5\text{mg/day}$ prednisone equivalent dose at start of study to $\leq 7.5\text{mg/day}$ prednisone equivalent by visitAchievement of reduction of corticosteroid dose from $>7.5\text{mg/day}$ prednisone equivalent dose at start of study to $\leq 7.5\text{mg/day}$ prednisone equivalent at Week 24 and maintaining low corticosteroid dose afterwards and achievement of BICLA response at Week 48
	
Achievement of reduction of corticosteroid dose from $>7.5\text{mg/day}$ prednisone equivalent dose at start of study to $\leq 7.5\text{mg/day}$ prednisone equivalent at Week 24 and maintaining low corticosteroid dose and achievement of prevention of moderate/severe BILAG flares (moderate/severe BILAG flare-free) at Week 48
	
Achievement of reduction in corticosteroid dose from $\geq 7.5\text{mg/day}$ prednisone equivalent dose at start of study to $\leq 5\text{mg/day}$ prednisone equivalent at Week 24 and maintaining low corticosteroid dose and achievement of BICLA response at Week 48Achievement of reduction of corticosteroid dose from $\geq 7.5\text{mg/day}$ prednisone equivalent

Objectives	Endpoints
	
dose to \leq5mg/day prednisone equivalent at Week 24 and maintaining low corticosteroid dose and achievement of prevention of moderate/severe BILAG flares (moderate/severe BILAG flare-free) at Week 48
 
• Total corticosteroid dose through Week 24, through Week 48, and from Week 24 through Week 48• Achievement of BICLA response by visit• Achievement of BILAG 2004 improvement without worsening by visit• Change from Baseline in BILAG 2004 score by visit• Achievement of BILAG 2004 shifts by visit• Achievement of BILAG 2004 improvement by organ system by visit• Achievement of maintained BICLA response by visit• Achievement of persistent BICLA response between Week 24 and Week 48• Worsening of any organ system with a BILAG 2004 B, C, D, E at Baseline to BILAG 2004 A or worsening of >1 organ system with a BILAG 2004 C, D, E at Baseline to BILAG 2004 B by visit• Achievement of BILAG 2004 C, D, E in all organ systems by visit• Change from Baseline in SLEDAI-2K by visit• Achievement of SRI 4, 6, 8 response by visit• Change from prior visits in S2K RI50 by visit• Change from Baseline in PGA by visit• Achievement of LLDAS status by visit

Objectives	Endpoints

To evaluate the ability of DZP as an add-on treatment to SOC medication to achieve organ specific endpoints	
Cumulative number of visits in LLDAS through Week 48Achievement of LLDAS Variant (demand for \leq5mg/day prednisone equivalent) in $>50\%$ of post-Baseline visits through Week 48Achievement of prednisone equivalent dose \leq7.5mg/day by visitPrednisone equivalent dose by visitOccurrence of severe BILAG 2004 flares by visitOccurrence of moderate BILAG flares by visitOccurrence of severe SFI flares by visitOccurrence of moderate SFI flares by visitTime to severe SFI flareTime to moderate SFI flareChange from Baseline in ACR/SLICC damage score by visitAchievement of DORIS remission by visitChange from Baseline in CLASI activity score by visit for all study participants and for subset of study participants with high CLASI scoreAchievement of a meaningful improvement in CLASI score by visit for all study participants and for subset of study participants with high CLASI scoreChange from Baseline in TJC and SJC by visit for all participants and for subset of participants with moderate to severe arthritisAchievement of a meaningful decrease in TJC/SJC by visit for all participants and for a subset of participants with moderate to severe arthritis

Objectives	Endpoints

 To evaluate the ability of DZP as an add-on treatment to SOC medication to achieve important patient reported outcomes 	
 Change from Baseline in Lupus Arthritis and Musculoskeletal Disease Activity score by visit Change from Baseline in FACIT-F by visit Change from Baseline in PHQ-9 score by visit Change from Baseline in FATIGUE-PRO 'Physical Fatigue', 'Mental Fatigue' and 'Fatigability' scores by visit Change from Baseline in LupusQoL by visit Change from Baseline in EQ-5D-5L by visit

 To evaluate the PK 	

 To evaluate immunogenicity of DZP as an add-on treatment to SOC medication To evaluate the PD and immunological parameters of DZP as an add-on treatment to SOC medication 	
 Incidence of anti-drug antibodies: [REDACTED] [REDACTED] Observed values and change from baseline in [REDACTED] [REDACTED] [REDACTED] [REDACTED] [REDACTED] in all study participants by visit and in study participants 'positive' at Baseline by visit
	
 Seroconversion of: [REDACTED] [REDACTED] status by visit

 To evaluate the safety and tolerability of DZP as an add-on treatment to SOC medication 	
 TEAEs leading to study withdrawal, TEAEs leading to permanent study medication discontinuation, TEAEs with start day on day or up to 1 day after infusion, other identified TEAE clusters Summary of participants withdrawn from the study due to TEAEs

Objectives	Endpoints
	
Summary of participants who permanently discontinued study medicationChange from Baseline in vital sign parameters by visitObserved values and change from Baseline in safety laboratory tests (hematology, serum chemistry, urinalysis) by visit, % study participants achieving critical threshold for selected lab parameters by visits

To evaluate changes in exploratory biomarkers	
Change from Baseline in biomarkers selected for analysis

To evaluate risk for anti-phospholipid associated events	
Change from Baseline in APS score by visit

ACR/SLICC=American College of Rheumatology/Systemic Lupus International Collaborating Clinics; [REDACTED]; APS=antiphospholipid antibody syndrome; BICLA=BILAG 2004-based Composite Lupus Assessment; BILAG=British Isles Lupus Assessment Group Disease Activity Index 2004; CLASI=Cutaneous Lupus Erythematosus Disease Area and Severity Index; DORIS=definitions of remission in SLE; DZP=dapirolizumab pegol; [REDACTED]; EQ-5D-5L=Euro Quality of life 5-Dimensions 3-Level; Fab'=fragment antigen-binding; FACIT-F=Functional Assessment of Chronic Illness Therapy Fatigue; FATIGUE-PRO=Fatigue patient reported outcome; Ig=immunoglobulin; LLDAS=low lupus disease activity state; PD=pharmacodynamics; PEG=polyethylene glycol; PGA=Physician's Global Assessment of Disease; PHQ-9=Patient Health Questionnaire-9; PK=pharmacokinetic(s); SFI=SELENA Flare Index; SJC=swollen joint count; SLE=systemic lupus erythematosus; SLEDAI-2K=Systemic Lupus Erythematosus Disease Activity Index 2000; sm=Smith antigen; SOC=standard of care; SRI4, 6, 8=Systemic Lupus Erythematosus Responder Index-4, 6, 8; [REDACTED]; S2K RI50=Systemic Lupus Erythematosus Disease Activity Index-2000 Responder Index-50; TEAE=treatment-emergent adverse event; TJC=tender joint count

4 STUDY DESIGN

4.1 Overall design

The study will be conducted to assess the efficacy, safety and tolerability of DZP in study participants with active SLE despite standard therapy and its results will support regulatory filing.

This study is a randomized, double-blind, placebo-controlled, parallel group, Phase 3 study in study participants 16 years of age and older with moderately to severely active SLE who are receiving stable SOC medication (ie, antimalarials, corticosteroids, and/or immunosuppressants) in line with local and international guidances at screening visit (V1). It will primarily investigate the improvement of SLE disease activity in study participants treated with DZP as add-on to nonbiological SOC treatment over 48 weeks. Key secondary objectives will be to investigate early improvement at Weeks 12 and 24, long-term disease control as evidenced by prevention of severe BILAG flares (severe BILAG flare-free) through Week 48, achievement of a

treat-to-target endpoint (low disease activity state in conjunction with low/acceptable corticosteroid dose [LLDAS]) through Week 48, and long-term improvement of disease activity as assessed with an instrument commonly used in clinical practice (SLEDAI-2K) at Week 48.

The study consists of a 2-week Screening Period, 48-week Treatment Period, and 6-week SFU Period (if the participant completes the study but decides not to enter the open-label extension study SL0046). Due to the required moderate to severe disease activity at screening visit (V1) and limited allowed treatment possibilities during the screening phase, a short Screening Period is planned. At the start of the study, eligible study participants will be randomized (2:1) to DZP 24mg/kg or to placebo administered by iv infusion Q4W. The initial dose will be administered as a 2-hour infusion while each subsequent dose will be administered as a 1-hour infusion. Study participants who complete the 48-week Treatment Period may be eligible to participate in the OLE study (SL0046). Study participants who withdraw early from the 48-week Treatment Period or choose not to enter the OLE will be followed up for at least 10 weeks SFU after their final dose of study medication.

Eligible study participants will have persisting active or relapsing-remitting SLE at screening visit (V1) despite stable SOC treatment (ie, antimalarials, corticosteroids, and/or immunosuppressants), in line with local and international guidance at screening visit (V1). Study participants considered to have a monophasic or an infrequent relapsing-remitting disease course (defined as no evidence for frequently flaring disease course and low risk to have frequent flares) will be excluded as their disease likely does not correspond to a persistent active or frequently relapsing SLE despite SOC treatment.

During the study, participants with a corticosteroid dose above a long-term tolerable level (7.5mg/day prednisone equivalent) will have to start corticosteroid tapering no later than the Week 8 Visit (Visit 4) to reach a target of 7.5mg/day or below. Investigators will be encouraged to start steroid tapering earlier if the condition of the study participant suggests improvement. Guidance will be provided on how to taper but the exact tapering regimen will be at the discretion of the Investigator to be adapted to the individual study participant's disease activity. Other SLE SOC treatment will have to be kept stable unless a reduction is indicated due to side effects. In case of insufficient improvement of disease activity, or a clinically relevant worsening of the disease activity, Investigators may initiate an escape treatment (Section 6.6.2) by increasing the dose of concomitant SOC medication. Depending on the nature of an escape treatment intervention, DZP may have to be discontinued if there is a safety concern. Investigators should discuss the impact of escape treatment use on study conduct with the Medical Monitor before initiation. In case of an initiation of escape treatment, study participants may be declared as **nonresponders** for the primary endpoint; however, they do not have to be withdrawn from the study.

Study participants will be encouraged to stay in the study under observation even if the study medication is discontinued (see Section 7.1). A study participant will have to be withdrawn from the study only if the study participant withdraws consent or a regulator, Institutional Review Board/Independent Ethics Committee (IRB/IEC), or the independent data monitoring committee (IDMC) requests a withdrawal for justified reasons (see Section 7.2).

An IDMC will be established to monitor the benefit-risk profile of study participants during the study. The IDMC will regularly review data and will have access to unblinded data as needed. The review will include observations in the BILAG 2004 neuropsychiatric body organ system in

order to monitor potential neuropsychiatric events falsely assigned to SLE. Details are described in the IDMC charter. The IDMC will provide recommendation if the study should be stopped, should be adapted or can proceed as planned.

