This study is a randomized, double-blind, placebo-controlled, parallel group, Phase 3 study in study participants 16 years of age and older with moderately to severely active SLE who are receiving stable SOC medication (ie, antimalarials, corticosteroids, and/or immunosuppressants) in line with local and international guidances at Screening Visit (V1). It will primarily investigate the improvement of SLE disease activity in study participants treated with DZP as add-on to nonbiological SOC treatment over 48 weeks. Key secondary objectives will be to investigate early improvement at Weeks 12 and 24, long-term disease control as evidenced by prevention of severe British Isles Lupus Assessment Group Disease Activity Index 2004 (BILAG) flares (severe BILAG flare-free) through Week 48, achievement of a treat-to-target endpoint (low disease activity state in conjunction with low/acceptable corticosteroid dose [low lupus disease activity state LLDAS]) through Week 48, and long-term improvement of disease activity as assessed with an instrument commonly used in clinical practice (Systemic Lupus Erythematosus Disease Activity Index 2000 [SLEDAI-2K]) at Week 48.

The study consists of a 2-week Screening Period, 48-week Treatment Period, and 6-week Safety Follow-up (SFU) Period. Due to the required moderate to severe disease activity at screening visit (V1), a short Screening Period is planned. At the start of the study, eligible study participants will be randomized (2:1) to DZP 24mg/kg or to placebo administered by intravenous (iv) infusion every 4 weeks (Q4W). The initial dose will be administered as a 2-hour infusion while each subsequent dose will be administered as a 1-hour infusion. Study participants who complete the 48-week Treatment Period may be eligible to participate in the open-label extension (OLE) study (SL0046). Study participants who withdraw early from the 48-week Treatment Period or choose not to enter the OLE will be followed up for at least 10 weeks after

their final dose of study medication (also referred to as investigational medicinal product [IMP] in the document).

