An IDMC will be established to monitor the benefit-risk profile of study participants during the study. The IDMC will regularly review data and will have access to unblinded data as needed. The review will include observations in the BILAG 2004 neuropsychiatric body organ system in order to monitor potential neuropsychiatric events falsely assigned to SLE. Details are described in the IDMC charter. The IDMC will provide recommendation if the study should be stopped, should be adapted or can proceed as planned.

Number of participants

Approximately 700 participants will be screened at approximately 230 sites in approximately 31 countries to achieve approximately 312 participants randomly assigned (2:1) to DZP 24mg/kg or to placebo for an estimated total of 208 and 104 participants in the DZP 24mg/kg and placebo groups, respectively.

[figure not shown]
Treatment groups and duration

This study consists of a 2-week Screening Period, a 48-week Placebo-controlled Period, and a 6-week SFU Period after Week 48 (>60 days [5 half-lives] after the final dose at Week 44), for a total of up to 56 weeks for study participants not entering the OLE study.

This document cannot be used to support any marketing authorization application and any extensions or variations thereof.

PUBLIC COPY

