1.3 Schedule of activities

Table 1-2: Schedule of activities

Period	Scr	Treatment (all visits in Treatment Period ±3 days)													SFU ^a
Visit	V1	V2	V3	V4	V5	V6	V7	V8	V9	V10	V11	V12	V13	V14	V15
Week	Scr	Bsl	W4	W8	W12	W16	W20	W24	W28	W32	W36	W40	W44	EOT ^b	EOS
Day ^c	D-14 to -1 ^d	D1 ^c	D28	D56	D84	D112	D140	D168	D196	D224	D252	D280	D308	D336	D378
Procedures															
Written informed consent	X														
Genetic informed consent ^e	X														
Demographics and Baseline characteristics ^f	X							X							
Thrombophilia diagnostic ^{g,dd}		X													
Inclusion/exclusion criteria ^h	X	X ⁱ													
General medical/procedures history	X														
Medication history ^j	X														
Vaccination history ^j	X														
Concomitant medications (inc. vaccines)	X	X	X	X	X	X	X	X	X	X	X	X	X	X	X
Pregnancy serum test	X														

Table 1-2: Schedule of activities

Period	Scr	Treatment (all visits in Treatment Period ± 3 days)													SFU ^a
Visit	V1	V2	V3	V4	V5	V6	V7	V8	V9	V10	V11	V12	V13	V14	V15
Week	Scr	Bsl	W4	W8	W12	W16	W20	W24	W28	W32	W36	W40	W44	EOT ^b	EOS W54
Day ^c	D-14 to -1 ^d	D1 ^c	D28	D56	D84	D112	D140	D168	D196	D224	D252	D280	D308	D336	D378
Procedures															
Pregnancy urine test (for WOCBP) ^{k,dd}		X	X	X	X	X	X	X	X	X	X	X	X	X	X
Antimalarial blood levels ^{dd}	X	X						X						X	
Chest x-ray ¹	X														
12-lead ECG ^m	X	X	X					X						X	
Vital signs	X	X ⁿ	X ⁿ	X ⁿ	X ⁿ	X ⁿ	X ⁿ	X ⁿ	X ⁿ	X ⁿ	X ⁿ	X ⁿ	X ⁿ	X	X
Study participant Identification Card assigned		X													
Randomization		X													
Infection serology ^o	X														
IGRA TB Test (QuantiFERON [®] at central lab) ^{dd}	X ^p													X	
TB questionnaire	X	X			X			X			X			X	
Complete physical examination and anamnesis ^q	X	X	X	X	X	X	X	X	X	X	X	X	X	X	X

Table 1-2: Schedule of activities

Period	Scr	Treatment (all visits in Treatment Period ±3 days)													SFU ^a
Visit	V1	V2	V3	V4	V5	V6	V7	V8	V9	V10	V11	V12	V13	V14	V15
Week	Scr	Bsl	W4	W8	W12	W16	W20	W24	W28	W32	W36	W40	W44	EOT ^b	EOS
Day ^c	D-14 to -1 ^d	D1 ^c	D28	D56	D84	D112	D140	D168	D196	D224	D252	D280	D308	D336	D378
Procedures															
Study withdrawal and study medication discontinuation criteria review			X	X	X	X	X	X	X	X	X	X	X		
BILAG 2004 ^r	X	X	X	X	X	X	X	X	X	X	X	X	X	X	X
SLEDAI-2K ^r	X	X	X	X	X	X	X	X	X	X	X	X	X	X	X
S2K-RI50			X	X	X			X			X			X	
PGA ^r	X	X	X	X	X	X	X	X	X	X	X	X	X	X	X
CLASI	X	X	X	X	X			X			X			X	
TJC/SJC	X	X	X	X	X			X			X			X	

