DZP=dapirolizumab; [REDACTED]; ECG=electrocardiogram; [REDACTED]; EOS=End of Study; EOT=End of Treatment; EQ-5D-5L=Euro Quality of life 5-Dimensions 5-Level; Fab'=fragment antigen-binding; FACIT-F=Functional Assessment of Chronic Illness Therapy-Fatigue; FATIGUE-PRO=Fatigue patient reported outcome; F/U=follow-up; HIV=human immunodeficiency virus; ICF=Informed Consent form; IEC=Independent Ethics Committee; Ig=immunoglobulin; IGRA= interferon- γ release assay; IMP=investigational medicinal product; INR=international normalized ratio; IWRS= Interactive Web Response System; LAMDA=Lupus Arthritis and Musculoskeletal Disease Activity; LLDAS=low lupus disease activity state; LTBI=latent tuberculosis infection; PEG=polyethylene glycol; PGA=Physician's Global Assessment of Disease; PGI-C= Patient Global Impression of Change; PGI-S=Patient Global Impression of Severity; PHQ-9=Patient Health Questionnaire-9; PK=pharmacokinetic; pTT=partial thromboplastin time; Q4W=every 4 weeks; QoL=quality of life; RNA=ribonucleic acid; Scr=Screening; SFI=SELENA Flare Index; SFU=safety follow-up; SJC=swollen joint count; SLE=systemic lupus erythematosus; SLEDAI-2K=Systemic Lupus Erythematosus Disease Activity Index 2000; SLICC =Systemic Lupus International Collaborating Clinics; S2K RI50=Systemic Lupus Erythematosus Disease Activity Index-2K Responder Index-50; TB=tuberculosis; TJC=tender joint count; TSH=thyroid-stimulating hormone; V=Visit; VAS=visual analog scale; W=Week; WOCBP=women of childbearing potential

Note: If study participants have a missed or delayed visit, they should return to their original visit schedule.

Note: For study participants prematurely terminating or completing the study, final disposition is recorded at Week 48 (V14, EOT). All study participants prematurely terminating from the study should be encouraged to undergo final evaluation procedures, in accordance with the Week 48 (V14, EOT) schedule as soon as possible after the final dose of study medication.

Note: Pandemic Situation: In case a study participant is unable to attend a scheduled visit due to pandemic related situations, all efforts will be taken by the Investigator to maintain contact with study participant remotely through telephone/video contact, monitor and support participant's safety and collect relevant study data.

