x The initial dose (Baseline; Day 1) will be administered as a 2-hour infusion as this will be the initial exposure to DZP. All other doses will be administered as a 1-hour infusion. Study participants will remain in the clinic for 1 hour post-infusion for observation. In study participants with an increased risk for allergic reactions premedication with antihistamines with or without paracetamol can be applied at the discretion of the Investigator. In case a study participant cannot attend a scheduled study visit or drug cannot be administered as planned at a scheduled visit the study drug should be administered as soon as possible but not less than 14 days before the next scheduled visit at a separate day. If procedures assigned to a certain visit have to be done on 2 separate days both days will be assigned to the same visit.

[figure not shown]
cc Study participants will receive a smart phone with the MyUCB4me tool to enter their corticosteroid use.

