2.3 Study design and conduct

2.3.1 Study description

The study will be conducted to demonstrate efficacy, safety and tolerability of DZP in study participants with moderately to severely active SLE despite stable nonbiological SOC medications (standard SLE therapy) and a persistent active or frequently relapsing remitting disease course or risk factors for relapsing remitting disease course to support regulatory filing.

The study is a randomized, double-blind, placebo-controlled, parallel group, Phase 3 study in study participants 16 years of age and older with moderately to severely active SLE who are receiving stable SOC medication (ie, antimalarials, corticosteroids, and/or immunosuppressants) in line with local and international guidance at Screening Visit (V1).

The study consists of a 2-week Screening Period, 48-week Treatment Period, and 6-week Safety Follow-up (SFU) Period (if the participant completes the study but decides not to enter the open-label extension (OLE) study SL0046). Due to the required moderate to severe disease activity at Screening visit (V1) and limited allowed treatment possibilities during the Screening phase, a short Screening Period is planned, see [Figure 2-1](#) below. At the start of the study, eligible study participants will be randomized (2:1) to DZP 24mg/kg or to placebo administered by iv infusion Q4W. The initial dose will be administered as a 2-hour infusion while each subsequent dose will be administered as a 1-hour infusion. Study participants who complete the 48-week Treatment Period may be eligible to participate in an OLE study (SL0046). Study participants who withdraw early from the 48-week Treatment Period will be followed up for at least 10 weeks after their final dose of study medication. Study participants who complete the study but choose not to enter the OLE will be followed up for at least 10 weeks after their final dose of study medication (ie, 10 weeks after last infusion at Week 44 which includes a 6-week SFU period).

Figure 2-1: Schema

BICLA=BILAG 2004-based Composite Lupus Assessment; BILAG=British Isles Lupus Assessment Group Disease Activity Index; BL=Baseline; CS=corticosteroid; DZP=dapirolizumab; EOS=End of Study; EOT=End of Treatment; N=number of study participants planned; OLE=open-label extension; PBO=placebo; Q4W=every 4 weeks; Scr=Screening; SFU=Safety Follow-up; SOC=standard of care; V=Visit; W/wk=week

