3.2 Analysis time points

The timeframe encompasses the entire study duration, which extends from Screening to 10 weeks after the final dose, ie, 48 weeks of the Double-Blind Treatment Period and 6 weeks of the SFU Period.

The following study periods will be included in the analysis (see Section 3.3 for the definition of Relative day):

- Screening Period: up to 14 days (Day -14 through Day -1).
- Double-Blind Treatment Period: 48 weeks, starts with the randomization (1:2) of eligible participants to 1 of 2 treatment arms (SOC + placebo [PBO] or SOC + DZP 24mg/kg), stratified in accordance with the 3 stratification factors (see Section 4.1). Study medication will be administered by iv infusion every 4 weeks, starting on Day 1.
- Safety Follow-up Period (SFU):
 - Participants who withdraw from the study prematurely will be followed up for at least 10 weeks after the last infusion.
 - Participants who complete the 48-week Double-Blind Treatment Period, but do not enter the OLE study will continue into a 6-week SFU Period (10 weeks after last infusion at Week 44). During this period, study participants will not receive study medication, but will be able to receive SOC treatment, as indicated.

The time points for individual assessments are provided in the schedule of activities in Section 1.3, Table 1-2 in the SL0043 protocol.

Analyses conducted by visit will include each planned study visit at which the assessment was scheduled. Data for planned study visits will be based on the nominal time point and will not include any unplanned visits. Usually, efficacy data will not be obtained at unscheduled visits, with the exception of lab data used in the BILAG grading process and for SLEDAI-2K. Here, labs that are obtained prior to the visit or up to 2 weeks after the original visit could be used to replace missing lab data (see separate Central BILAG Grading and Adjudication Plan for details on the BILAG grading process).

All data collected, including assessments (planned or unplanned) will be reported in participant data listings. Data from participants withdrawing from the study early at end of treatment (EOT) visits will be mapped to the next scheduled visit per assessment for purpose of analyses and inclusion in summary tables but will be presented in terms of nominal visit in listings.

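### Completers who do not enter the OLE are promised at least 10 weeks of follow-up after the last dose, but End of Study is fixed at Day 378, which gives 70 days only if the Week 44 infusion is not late

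*Protocol*

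**What the plan says.** The minimum is stated in several places. Protocol Section 4.1 covers early withdrawers and those completers who "choose not to enter the OLE will be followed up for at least 10 weeks SFU after their final dose of study medication". The Synopsis (Section 1.1, Overall design) gives the same 10-week minimum. SAP 2.3.1 repeats it for completers and explains it as "10 weeks after last infusion at Week 44 which includes a 6-week SFU period". SAP 3.2 says that these completers "will continue into a 6-week SFU Period (10 weeks after last infusion at Week 44"). The Synopsis also describes the same period, under treatment duration, as a "6-week SFU Period after Week 48 (>60 days [5 half-lives] after the final dose at Week 44").

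Table 1-2 (Section 1.3) gives nominal days: Week 44 is Day 308, Week 48 is Day 336 and End of Study (V15, Week 54) is Day 378. Its ±3-day window is stated for the Treatment Period only; the safety follow-up column shows no window.

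Two rules bear on a late dose. Footnote x says that, if dosing cannot go ahead as planned, "the study drug should be administered as soon as possible but not less than 14 days before the next scheduled visit at a separate day". A Note to the same table says: "If study participants have a missed or delayed visit, they should return to their original visit schedule". Section 6.4 repeats the return to schedule. It also refers dosing deviations to the Medical Monitor for possible schedule adjustments, case by case.

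**The concern.** The promised minimum runs from the participant's own final dose, whereas V15 is a calendar visit. The two agree exactly when the Week 44 infusion is on time and diverge by one day for each day it is late. The protocol permits late dosing and then directs the participant back to the calendar, so a site that follows the schedule can miss the stated minimum.

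What is at stake is safety follow-up. Section 8.3.1 collects adverse events until the follow-up visit. SAP 10.1 counts events as treatment-emergent up to 60 days after the last dose, and SAP 10.2 credits every participant with those 60 days as time at risk. If V15 comes before day 60, the analysis counts days in which new non-serious events are no longer being collected.

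**Working it through.** **Inputs.** Week 44 = Day 308, Week 48 = Day 336, End of Study = Day 378, window ±3 days (Table 1-2). A late dose must be at least 14 days before the next scheduled visit (footnote x). Promised minimum: 10 × 7 = 70 days (Section 4.1). Synopsis criterion: more than 60 days (Section 1.1). Treatment-emergent window: last dose + 60 days (SAP 10.1).

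**The plan's own figures reproduce.** 378 − 308 = 70 days = 10 weeks, and 378 − 336 = 42 days = 6 weeks.

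**Latest permitted Week 44 infusion.** By the window: 308 + 3 = Day 311. By footnote x: 336 − 14 = Day 322.

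**Follow-up if V15 stays at Day 378** (378 − infusion day):

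| Week 44 infusion | Days to Day 378 | Short of 70 by | More than 60? | Day 60 after dose | V15 before window closes by |
|---|---|---|---|---|---|
| Day 308 | 70 | 0 | yes | Day 368 | 0 |
| Days 309–311 | 69–67 | 1–3 | yes | Days 369–371 | 0 |
| Days 312–317 | 66–61 | 4–9 | yes | Days 372–377 | 0 |
| Day 318 | 60 | 10 | no | Day 378 | 0 |
| Days 319–322 | 59–56 | 11–14 | no | Days 379–382 | 1–4 |

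**Other reading: V15 falls 42 days after the actual Week 48 visit.** Across the ±3-day windows, follow-up runs from 333 + 42 − 311 = 64 days to 339 + 42 − 305 = 76 days. A dose 14 days before the Week 48 visit gives 14 + 42 = 56 days. The shortfall remains, with the same minimum.

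**Can a dose on Day 322 arise?** Section 8.2.7 suspends dosing until at least 14 days after a known COVID-19 contact. A contact on Day 308 makes 308 + 14 = Day 322 the earliest dose, which is also the footnote x limit.

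**Time at risk, Day 322 dose, first dose on Day 1.** SAP 10.2 gives (322 − 1) + 60 = 381 days. From first dose to V15 is 378 − 1 = 377 days. The excess is 4 days, and 4/381 is about 1% for that one participant.

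**The case against.** The strongest reply is that the minimum is itself a rule anchored to the dose. Section 4.1 counts from the final dose, and its sentence also covers early withdrawers, for whom Day 378 cannot be the anchor. Footnote a, on the follow-up column, waives the visit according to how long before Week 48 the drug was stopped. Protocol 9.2.2 describes the study as running to 10 weeks after the final dose. Table 1-2 sets no upper limit on V15, and Section 6.4 allows for schedule adjustments. A site could therefore delay V15 and keep the promise, and the return-to-schedule Note is only a general instruction.

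Much of this stands. A reader might infer that the protocol forbids a later V15; the text does not say so. But Section 8 requires adherence to the Schedule of Activities, and both the Note and Section 6.4 point back to it. No visible passage says that V15 moves with the last dose, although some Table 1-2 footnotes are missing from the public copy. SAP 2.3.1 and 3.2 treat 6 weeks after Week 48 and 10 weeks after the last infusion as the same thing, which is true only for an on-time Week 44 dose.

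A reader might also infer an arithmetic error. There is none: the nominal days agree with the promise. Nor should one build a worse case by moving Week 48 late while leaving V15 at Day 378. That mixes two anchors, and footnote x counts from the scheduled visit.

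**Conclusion.** The point holds as a minor internal inconsistency. With V15 at Day 378, the 70-day minimum is met only if the Week 44 infusion is on or before Day 308. Permitted delays leave 67 to 69 days within the window and as few as 56 under footnote x. This assumes that sites follow the return-to-schedule instructions literally and that no unseen footnote moves V15.

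The consequences are small. The protocol gives two figures for five half-lives, more than 60 days (Section 1.1) and 10 weeks (Section 8.2.4). Every in-window delay, and any dose up to Day 317, still satisfies the first. Doses on Days 318 to 322 do not, and only those on Days 319 to 322 cut into the treatment-emergent window, by 1 to 4 days.

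A reader might infer a material bias in the safety results, but the documents do not support that. The possible loss is new-onset non-serious events in those few days, since Section 8.3.1 also requests serious events after the end of the study. The 1% excess is one late-dosed participant's time at risk, not a trial-level figure. The documents do not say how many completers would decline the OLE and also be dosed this late; the number is likely to be small. Efficacy is unaffected.

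**What to change.** In the V15 column of Table 1-2, state for completers not entering the OLE: *Week 54 (Day 378) or 70 days after the actual last infusion, whichever is later*. Say that the return-to-schedule instruction, in the Note and in Section 6.4, does not apply to V15. Leave footnote a as it is. Use the same V15 wording in SAP 2.3.1 and 3.2. Because 70 days exceeds 60, this also closes the gap with SAP 10.1 and 10.2.

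The cost is a later V15 for the few completers dosed late: Day 311 + 70 = Day 381 (3 days later) and Day 322 + 70 = Day 392 (14 days later). No visit, procedure or participant is added. If the last participant in the study is one of them, the end of the study moves by the same number of days.
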